#### Set-up

At MSAS, the research coordinator will set VPAP Adapt to assigned mode and prescribed pressure settings. Patient will be introduced to device/humidifier and educated on use and proper maintenance. A prescription will be sent to a DME company for additional PAP mask and supplies. Interim equipment from MSAS will be used for initial set up. Common PAP and mask issues will be discussed with the participant as well as how we will be able to help them address these issues if needed, including the role of mask liners (e.g. REMzzz or padacheek) among those complaining of skin or other facial irritation, redness, or soreness.

Common barriers that arise soon after set-up most likely involve mouth breathing, mask leak, and air swallowing (aerophagia). Patients will be informed prophylactically about these issues so they can address them as they arise during the titration or shortly thereafter. It is not uncommon for these factors to arise over time and will be dealt with through aggressive follow-up (see Special Considerations below).

Participants will be instructed on how to fill out the daily online sleep diary. All Follow-ups and titrations will be scheduled at this time. Research coordinator will document PAP setting, PAP pressure, mask type, and other relevant information from this encounter.

## Follow-up Appointments

The goal is to achieve the maximum number of participants using the device. To reiterate, all participants are required to attend a total of seven follow-up appointments (2 full night studies after initial titration, 4 data download and progress appointments, and final data download and progress appointment with an exit interview). Additional follow-up appointment frequency will vary based on individual needs. All follow-up will be documented by research coordinator.

### *Online Follow-up*

#### Sleep Diary

A sleep diary will be available online for patients to fill out daily. The sleep diary tracks subjective: bed time (BT), sleep onset latency (SOL), wake after sleep onset (WASO), total sleep time (TST), time in bed (TIB), out of bed time (OOB). They will also complete an 8-item Likert scale for sleep quality ratings in the morning as well as the Global Morning Rating of Nightly Sleep where patients rate their sleep on a 0-100% scale. The last question will be a rating on our PUDS scale to assess distress or lack thereof in using PAP therapy. Patients will be prompted to indicate if something has changed, such as medications, when they fill out this daily diary.

### *Clinic Follow-up*

All participants are required to attend 5 clinic follow-up visits with a clinical research coordinator (refer to flowchart). The first is 10-14 days after set-up, the second is 10-14 days after their first follow-up, the third is 10-14 days after titration #2 (see below), fourth is 10-14 days after third follow-up, and final follow-up is 14-28 days after titration #3. These clinic follow-up visits will consist of: data download, outcomes, and qualitative measure of the participants progress.

#### Data Download

Objective data will be downloaded from the device.

#### Outcomes and Scales

ISI, III, ESS, FSS, QLESQ, FOSQ-10, VAS-F, VAS-S, HSCL, SDB-6

Patient Global Assessment scale, Adverse Effects Checklist, NOSE-8,

#### Qualitative Measure

This includes a discussion with patient regarding their progress and experiences with PAP. Are they receiving any benefits? Do they feel differently? We will also address anything noted on Outcomes and Scales that suggests a problem or barrier has arisen or remains unresolved.

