## **Summary of Endpoint Objectives:**

### **Primary Endpoint objectives:**

- Change in insomnia severity from baseline to 4 months as measured by the Insomnia Severity Index (ISI)
- Sleep Diary sleep quality rating (8 point Likert scale)
- Global Morning Rating of Nightly Sleep (0-100% scale)
- Change in prospective sleep log data for insomnia parameters (SOL, WASO, SE)

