## **Subject Recruitment and Eligibility:**

All adult insomnia patients presenting at MSAS are potential candidates for this study. Potential participants are pre-screened to identify likely candidates. Medications need to be clarified and a discussion regarding possible upcoming medication changes/adjustments is necessary. The patients' travel plans for the next 3-6 months need to be discussed: length of trip, time zone changes, and dates of trip. Does the patient have computer access and will they be able and willing to complete daily 5min online tasks? Evaluate the patient's transportation situation and ability to return to the facility for follow up visits. Certain medical conditions or lifestyle habits may exclude patients from the protocol, including but not limited to: asthma, COPD, RLS, PLMD, smoking, epilepsy. Query mental or medical health problems and any upcoming procedures that may interfere with research protocol including surgery or elaborate testing that may affect sleep and decide if it is possible to work around these dates. Besides talk therapy, determine whether there are any plans for shock therapy or other brain stimulation that may affect sleep physiology. Have they recently started or do they plan to start insomnia treatment within the next few months (aside from coming to our sleep center for insomnia help)?

Participants who are currently treating their insomnia are eligible for the protocol as long as they maintain (or decrease/cease) the same treatment program throughout participation. Example: a patient taking sleep aids may continue to take sleep aids or decrease their dose but may not increase the dose or add another treatment, such as cognitive therapy, during involvement with this protocol.

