### **Follow-up Visits**

Participants will return every 2 weeks following their titration study for a follow-up clinic appointment conducted by sleep technologist with availability of [name] for relevant Q&A with patient. The following will be completed at each follow-up appointment:

1. Outcomes: Subject completes the following questionnaires:
  - a. Validated research instrument for tracking insomnia: ISI
  - b. Sleep related impairment: ESS, VAS-F, VAS-S, III, FSS, SDB-6
  - c. Quality of Life/Impairment: FOSQ-10, QLESQ, HSCL
  - d. PAP Therapy Tracking Tools: AEC, NOSE-8
  - e. Change Tracking Tool: PGA (Insomnia, Sleep Quality, Fatigue, Sleepiness, Energy level)
2. Data, download from the VPAP Adapt.
  - a. Usage
  - b. AHI, flattening %
3. Review device usage. Address concerns or questions including:
  - a. Progress and experiences with PAP
  - b. Benefits or lack thereof
4. Review sleep diary.
5. Determine if the subject has had any adverse events or adverse device effects.
  - a. Troubleshoot as needed

**Summary:** Following initial titration, the following steps will reoccur for the remainder of the protocol (refer to initial flow chart to see repetition of steps):

- Patients return on weeks 2 and 4 for Follow-up visits
- On week 6 they repeat titration process and complete Follow-up visit surveys and downloads
- Return on weeks 8 and 10 for follow-up appointments
- Return on week 12 for a final titration

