## Final Datasets

Following the final titration, participants will return between weeks 14 and 16 to meet with a research coordinator to obtain a final data download and complete final outcomes questionnaires. This meeting also includes: follow-up care program, exit interview, scheduling into the clinical venue, opportunity to try other mode of PAP therapy, clarifications regarding the free equipment, and reimbursement for travel.

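### Visit staff not blinded to PAP mode review the diary and follow up problem answers on the ISI, leaving the self-reported primary outcomes open to an arm-dependent reporting bias of unknown size

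*Combined protocol and SAP*

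**What the plan says.** The Primary Endpoint objectives are the change in ISI to four months, the diary sleep-quality rating, the global morning rating, and diary SOL, WASO and SE. All are self-reported.

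Under Follow-up Visits (Phase 3), the patient completes the ISI and the other scales. Staff download the device, go over usage and perceived benefit, and carry out the item "Review sleep diary". Under Clinic Follow-up, the Qualitative Measure paragraph has staff ask whether the patient is benefiting and feels different, and then states: "We will also address anything noted on Outcomes and Scales that suggests a problem or barrier has arisen or remains unresolved". The Outcomes and Scales list just above it begins with the ISI. Phase 4 repeats the Follow-up Visits steps at exit, where the final ISI is collected.

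Follow-up Visits assigns these appointments to a sleep technologist, and Clinic Follow-up to a clinical research coordinator. According to Set-up, "the research coordinator will set VPAP Adapt to assigned mode and prescribed pressure settings". According to the Titration Procedure, technologists titrate in the assigned mode. The only person described as blinded is the independent PSG scorer (Titration #1 and Polysomnography). The hypothesis at the end of the Background is that ASV will reduce insomnia severity more than CPAP.

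**The concern.** When an outcome is the patient's own rating, the rating can be influenced by whoever discusses it with the patient. A patient who finds that low ratings lead to questions, or that good ones are welcomed, may rate differently next time. If the staff know the mode and expect one arm to do better, that influence need not be equal in the two arms. An unequal influence adds directly to the estimated treatment difference.

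The protocol already accepts this principle for PSG, where the scorer is blinded to protect the measurements. The PSG indices are secondary endpoints. The primary endpoints are more open to influence and have no corresponding safeguard. The route is also distinct from whether patients know their own mode, because it works through the staff.

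**Working it through.** The plan states no figure on this point, so there is none to reproduce. The check is a reading of the sections, followed by an illustration of scale.

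**Reading**

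1. *Are the primary outcomes self-reported?* Yes, all of them.
2. *Do staff see and discuss them?* Diary review is an explicit item at each follow-up appointment, and the diary carries the sleep-quality rating, the global rating and the inputs to SOL, WASO and SE. For the ISI, discussion is conditional: staff take up answers that point to a problem or barrier.
3. *Do those staff know the mode?* This is inferred from their roles. Coordinators set and document the mode, and technologists titrate in it. No section blinds either role during follow-up.
4. *Is there an expectation that differs by arm?* Yes. The Background hypothesizes ASV superiority, and Titration #1 anticipates less pressure intolerance with ASV.
5. *Is rating separated from discussion?* No section requires the questionnaires to be finished before staff contact or before the download is reviewed.
6. *What protection exists?* Patients enter data directly into the database (Data Collection and Storage), and the diary is completed online each morning. This stops staff altering an entry. It does not stop a discussion at one visit from affecting later ratings.

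**Illustration of scale**

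Inputs:
- 25 patients per arm and two-sided 0.05, from Power Analysis and Sample Size.
- SD back-calculated from the two ASV series in the Background: (16.8 − 9.7)/1.40 = 7.1/1.40 = 5.07, and (19.0 − 11.9)/1.50 = 7.1/1.50 = 4.73.
- A reporting shift b between arms, which is assumed, with a true difference of zero.

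Formulas: d = b/SD. Non-centrality λ = d × √(25/2) = 3.536 d, with 48 degrees of freedom. Rejection rate = P(|T| > t₀.₉₇₅,₄₈), where T is non-central t with parameter λ.

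For b = 1, d = 1/5.07 = 0.197 (λ = 0.70) or 1/4.73 = 0.211 (λ = 0.75). The rejection rate is 10.5% or 11.3%.

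| Assumed shift (ISI points) | d | Rejection rate, true difference zero |
|---|---|---|
| 0 | 0 | 5% |
| 0.5 | 0.099–0.106 | 6.3–6.5% |
| 1 | 0.197–0.211 | 10.5–11.3% |
| 1.5 | 0.296–0.317 | 17.6–19.5% |
| 2 | 0.394–0.423 | 27.7–31.0% |
| 3 | 0.592–0.634 | 53.6–59.3% |

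The planned net effect of 0.80 SD is 0.80 × 4.73 = 3.8 to 0.80 × 5.07 = 4.1 points, so one ISI point is about a quarter of it.

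**The case against.** Several points on the other side have force.

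- *The ISI wording is conditional.* A reader might infer that staff work through every ISI answer at every visit. The text does not say so. It covers answers that suggest a problem or barrier, and elsewhere the protocol uses barrier for difficulty in adapting to PAP. The AEC is the one instrument expressly described as a discussion aid, so staff could follow the paragraph without raising an ISI answer. This stands as a limit on the claim. It does not remove the exposure, because the instruction covers the whole list and excludes nothing on it.
- *The diary has other uses.* It also holds PUDS and the medication-change prompt, which staff need. That is a reason to keep those fields in use at the visit, but not the sleep ratings.
- *Frequency.* Contacts are about every two weeks, but Clinic Follow-up counts five clinic visits. The qualitative discussion is not described for the titration nights.
- *Order of steps.* A reader might infer a contradiction, because Follow-up Visits puts questionnaires first while Clinic Follow-up says "These clinic follow-up visits will consist of: data download, outcomes, and qualitative measure of the participants progress" and Final Datasets says "to obtain a final data download and complete final outcomes questionnaires". The latter two list contents and set no sequence. What holds is that the order is not fixed anywhere.
- *Care.* The patient "may not increase the dose or add another treatment, such as cognitive therapy, during involvement with this protocol", so ISI answers should not prompt added insomnia treatment. They could still prompt PAP troubleshooting, so it would be too strong to say that they have no bearing on care.
- *The figures.* The SDs come from single-group before-and-after effect sizes whose denominator is not stated. The planned test is a group-by-time interaction, which depends on the SD of change. The table shows what any shift of a given size would do, not what this practice adds beyond the general lack of blinding. That stands.

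**Conclusion.** The concern holds as a matter of exposure. Staff whose roles give them knowledge of the mode review diary data that include primary endpoints, and are told to act on problem answers from a list headed by the ISI, under a stated hypothesis that favours one arm. The plan has no safeguard against this for the primary outcomes.

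A reader might go further and infer that the trial will be biased towards ASV by one or two points. The documents do not support that: they give neither a size nor a direction. The figure of about 11% for a 1-point shift rests on the assumed shift, on SDs of 4.7 to 5.1 and on 25 per arm, and serves only to show that a small shift would matter. That the staff know the mode is a strong inference from their roles, not an explicit statement. The change is worth making because it protects the primary outcomes at very little cost.

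**What to change.** Amend Follow-up Visits, Phase 4: Exit Interview, Clinic Follow-up, Qualitative Measure, Titration #2 and Final Datasets to state two things:

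1. At every visit at which questionnaires are due, including exit, the patient submits the ISI and the other questionnaires directly into the database before any staff contact or download review.
2. Staff do not discuss ISI answers or diary sleep ratings with the patient. PAP troubleshooting draws on the AEC, NOSE-8, PUDS and the download. The diary's medication-change prompt, the HSCL and any other safety-relevant answers remain available to staff.

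Hiding all efficacy scales from staff until database lock is not needed for this and would be debatable, since some of them may inform care.

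The cost is protocol wording and a visit routine. The small downside is that staff lose the ISI and the diary ratings as a conversation aid. The change reduces the bias route but does not close it: unmasked staff may still ask open questions about benefit, and any knowledge that patients have of their own mode remains. The trial report should state both limits.

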## Titration #2 (Repeat)

All participants will be required to undergo a full night retitration 6 weeks following set-up. In order to test this efficacy hypothesis accurately, retitrations are necessary every 6 weeks. In our clinical experience, we have found that pressures need to be adjusted frequently as patients adapt to PAP therapy. Physical changes in the airway during the adaptation process

require fine tuning of pressure settings of usually 1-2cmH2O. The two retitration studies (at 6wks and 12wks) are key components to ensuring participants are using the most optimal pressure settings as they progress through the adaptation process. Data will be downloaded from each device at these studies and patients will complete all Follow-up outcomes and scales.

#### Titration #3 (Final)

The final titration study will not only serve as an opportunity to reevaluate pressure needs but also to measure sleep indices: sleep onset latency, wake after sleep onset, sleep as proportion of TIB, sleep efficiency, sleep architecture, AHI, RDI, CAI, etc. This comparison will serve as the main pre and post objective comparison of data, because we anticipate the patient's adaptation to the device to be approaching an optimal point, and therefore, the objective metrics would most likely show the most well consolidated sleep compared to baseline. However, in some cases, pressure tweaks may still be needed, which then permits opportunity for another minor adjustment of the device. The patient then will be permitted to use these new settings for the next two to four weeks before the exit interview. This two to four week period then is quite important for that proportion of patients where pressure settings were still not optimal until undergoing the third titration. For some, if the minor pressure tweaks approach optimal, we will see noticeable therapeutic gains in that final few weeks of use on the new settings.

#### Supplemental Follow-up/Care

##### *PAP Nap*

The PAP-Nap is our daytime abbreviated cardio respiratory desensitization study. Participants who are having difficulty adapting to any aspect of PAP may benefit from this procedure to help trouble shoot barriers. The individualized attention allows patients to be introduced to PAP in a gradual fashion with increased attention from a sleep technologist. PAP Naps can also be used to address mask and intolerance issues. This PAP Nap can occur at any time during the treatment, based solely on patient problems with compliance, and it often is an intervention that specifically can reduce drop-outs. The number of PAP Naps per each patient will be limited to one. In special circumstances, a patient may need an extended PAP Nap conducted at night.

##### *Phone Consult*

Participants will have access to research assistants (and sleep technologists) during the day to discuss or troubleshoot any issue that may come up during the course of the protocol, and as described on the Informed Consent Form, [name] can be contacted during the overnight hours if needed. By having access to these resources, we hope to help patients adapt to PAP and use PAP nightly.

##### *Clinic Follow-up*

Extra daytime follow-up to address any issues that need hands on attention (like mask issues) will be available to participants as needed.

## Special Considerations

### *Mask Issues*

Common mask issues will be discussed with the patient during Set-up as well as first line trouble shooting for each problem. For mouth breathing or mouth leak, the chinstrap will be demonstrated. For mask leak, proper mask fit, tightening the mask, chinstrap, and mask liners will be discussed. Mask liners will also be recommended for soreness, mask creases, and pressure spots. Due to the nature of this study and its short duration, it is necessary to expedite care of these issues that may be barriers in rapid acclimation to PAP. A lack of reasonably rapid acclimation will skew the results toward less than optimal outcomes, therefore the above items will be addressed both prophylactically and as they arise.

### *Aerophagia*

Aerophagia, or air swallowing, is a complication with PAP therapy that can be very uncomfortable or even painful. We would like all participants to be aware of aerophagia and bring this symptom to our attention immediately. Leg jerks, mask issues, reflux, NAR, and pressure intolerance can all cause aerophagia and will require clinical attention.

### *Leg Jerks (sub cohort potential)*

Patients who did not report restless leg or periodic limb movement symptoms on their intake, but had significant leg movements during their PSG (not respiratory related) may be excluded from the study if they continue to show leg jerks on their titration study. Patients who do not report leg movement symptoms on their intake and do not exhibit leg movements on their diagnostic PSG but do exhibit leg jerks on any titration study, will require careful re-evaluation of clinical care by [name] to determine if leg jerks are a medical issue requiring withdrawal from the study.

## Final Datasets

Following the final titration, participants will return between weeks 14 and 16 to meet with a research coordinator to obtain a final data download and complete final outcomes questionnaires. This meeting also includes: follow-up care program, exit interview, scheduling into the clinical venue, opportunity to try other mode of PAP therapy, clarifications regarding the free equipment, and reimbursement for travel.

### *Follow up care program*

Patients will be instructed to continue follow up as needed for treatment of their SDB and Insomnia. They will be transitioned into the patient population standard of care at MSAS or to another sleep center of their choosing. Patients may choose for referral for an alternative SDB treatment option.

### *Exit interview*

Patients will undergo an Exit Interview and will be queried on five general topics: 1) general study overview; 2) PAP effectiveness; 3) PAP and sleep medication; 4) long-term treatment of sleep-disordered breathing; and 5) PAP devices and masks. Questions the

participant may have for us are addressed at this time. Any final measures and paperwork will be completed.

#### *Final Dataset of RCT*

The final dataset comprises those participants in 14 to 16 week window and will be used for the primary research paper for this study to address the comparison between CPAP and ASV in the treatment of SDB events among chronic insomnia patients as well as the resultant outcomes from these distinct therapies.

#### *Six month follow-up*

Outside of the research project, all participants will be scheduled for a 6 month follow up to track their progress with PAP therapy and their Insomnia. During this time, although there will be no formal cross over study, we will clarify which patients intend to continue to PAP use and in which mode, which means that some patients may have changed to a different mode after the completion of the RCT protocol. As such, patients originally assigned to CPAP may need to undergo a PSG titration study to find the most accurate pressures or to qualify for ASV therapy as it relates to their insurance coverage. We will strongly recommend this course of treatment to relevant patients. Then at the 6 month mark we will compile any available data from the cohort that continues using in preparation for a case series report, if such data offers scientific value. Otherwise, our main focus by the six month follow-up is to maintain continuity of care to insure a proper transition from the research venue to the clinical care model.

